### **11.2.1 Physical examination**

At the Screening visit, all subjects will undergo a physical examination, including but not limited to assessment of general appearance and skin, head/ eyes/ ears/ nose/ throat, respiratory system, spleen, liver and lymph nodes.

### **11.2.2 Symptom-directed physical examination**

A symptom-directed physical exam will be performed at all visits, except screening. If a symptom is reported, a system-based assessment will be performed, if needed, for a detailed

check of the affected body system. Any symptom reported, including worsening of existing conditions, will also be recorded as an adverse event.

### **11.2.3 Vital signs and body temperature**

Systolic and diastolic blood pressure and pulse as well as body temperature will be recorded at all visits with the subject at rest in a sitting position.

### **11.2.4 Local and systemic tolerability**

The local tolerability (i.e., injection site reaction) must be inspected and evaluated by the investigator one hour after each vaccination (for treatment group M1 and M2 starting after the first vaccination on day -28 and for groups A-D starting on day 0 after their first injection). Additionally, the local tolerability (i.e., inspection of the previous injection site) will be performed prior to application of the subsequent study treatment, if applicable (for treatment group M1 and M2 this examination starts before the second vaccination on day 0 and for groups A-D on day 28). Furthermore, local tolerability will be evaluated by the subjects after the vaccination in the subject diaries over a period of 7 days after each treatment (see section 0). Grading will be performed according to the respective FDA Guidance for Industry (3), modified, reflecting the guidance of the Brighton Collaboration:

**Table 8 Grading of local reactions**

Local reaction to injectable product	Mild (grade 1)	Moderate (grade 2)	Severe (grade 3)	Potentially life threatening (grade 4)
Pain	Does not interfere with activity	Interfere with activity or repeated use of non-narcotic pain reliever	Prevents daily activity or repeated use of non-narcotic pain reliever	Emergency room (ER) visit or hospitalization
Tenderness	Mild pain to touch	Pain with movement	Significant pain at rest	ER visit or hospitalization
Erythema/Redness*	≤ 5 cm	5.1–10 cm	> 10 cm	Necrosis or exfoliate dermatitis
Swelling**:	≤ 5 cm and does not interfere with activity	5.1–10 cm or interfere with activity	> 10 cm or prevents daily activity	Necrosis
Itching	Does not interfere with activity	Interferes with activity or repeated use of non-narcotic pain reliever	Prevents daily activity or repeated use of anti-inflammation and pain-relieving ointment	Emergency room (ER) visit or hospitalization
Induration*	≤ 1 cm Does not interfere with activity	> 1 to < 3 cm Interferes with activity or repeated use of non-narcotic pain reliever	≥ 3 cm Prevents daily activity or repeated use of anti-inflammation and pain-relieving ointment	Not applicable

\* In addition to grading the measured local reaction at the greatest single diameter, the measurement should be recorded as a continuous variable.

\*\* Swelling should be evaluated and graded using the functional scale as well as the actual measurement.

Findings in the local tolerability examination by the investigator as well as local tolerability findings recorded in the subject diary will be covered separately as adverse events.

Diary solicited systemic (i.e., systemic tolerability) AEs include: Nausea/vomiting, headache, fatigue, and myalgia, also to be documented in the eCRF. In addition, body temperature will be assessed daily for 7 days and fever will be graded. Grading will be performed according to the FDA Guidance for Industry (3).

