### **Safety Analysis:**

Vital sign checks including measurement of blood pressure, pulse rate and axillary body temperature as well as physical examination were performed at all visits. Additionally, the injection site was inspected and evaluated for local side effects by the investigator at each visit and before and 6 hours after each vaccination. Grading of local pain, tenderness, redness, swelling, itching and induration was performed according to the respective FDA guidance for industry and the guidance of the Brighton Collaboration. Accordingly, local side effects were graded as mild (grade 1), moderate (grade 2), severe (grade 3) and potentially life-threatening

(grade 4). All participants were provided with a template that allows estimation of local reactions (supplementary information).

Pain, itching and induration were graded as mild if they did not interfere with daily activity, as moderate if they did compromise activity or necessitated repeated use of non-narcotic pain reliever/anti-inflammatory and pain relieving ointment (itching and induration) and as severe if they prevented daily activity. Grade 4 pain/itching included the need for Emergency room (ER) visit or hospitalization. Swelling and erythema below a diameter of 5 cm were rated as mild. Swelling/erythema exceeding 10 cm in diameter were considered to be severe and necrosis indicated grade 4 swelling/erythema (supplementary information).

Furthermore, participants were requested to keep a study diary in order to record all local and systemic symptoms and any adverse event occurring during the first two weeks after vaccination starting with the first entry 6 hours ( $\pm 1$ ) after vaccination. The subjects themselves recorded the assessments once daily at the same time each day. Completeness and accuracy of self-reported symptoms and side effects were verified at each visit by a study-related physician. Diaries were reviewed together with the particular participant at each visit and participants were interviewed for any adverse events. Diaries had to be signed by both the particular participant and the reviewing physician at the end of each vaccination period to confirm and ensure completeness and reliability of self-reporting. The investigator collected the diaries at each visit and new ones were dispensed after vaccination.

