Solicited and non-solicited adverse events (AEs) were reported separately. Solicited AEs included pyrexia, flu like illness, headache and injection-site- related side effects (erythema, swelling, induration and pain).

In general, MV-CHIK vaccine had an acceptable tolerability profile. All adverse events observed were treatment emergent AEs and were recovered without any sequelae before or at study end.

The most frequently solicited AEs were headache (57.1%), injection side pain (50.0%), influenza like illness (45.2%), vaccination side pain (40.5%), fatigue (38.1%), nausea (31.0%), myalgia (26.2%) and arthralgia (23.8%). The most frequently related solicited AEs were injection side pain (50.0%), vaccination site pain (40.5%), headache (28.6%) and fatigue (23.8%).

Unsolicited AEs were AEs with none of the preferred terms of solicited AEs. 28 subjects (66.7%) had a total of 73 unsolicited AEs. Two subjects (4.8%) had two severe unsolicited AEs, five subjects (11.9%) had seven related unsolicited AEs and 19 subjects (45.2%) reported 33 unsolicited AEs where an action was taken. Two subjects (4.8%) reported two serious unsolicited AEs. The most frequently unsolicited AEs were nasopharyngitis (26.2%) and oropharyngeal pain (11.9%).

Special attention was directed to any occurrence of joint pain during the MV-CHIK study due to significant joint pathology caused by CHIKV. The subjects were asked to report any symptoms of joint pain in their subject diary and they were asked for any symptoms during each visit. Overall, 23.8% (10/42) of the subjects reported any signs of joint pain or arthralgia during the treatment period, 11.9% (5/42) of which were rated as related to the study treatment. In all 5 cases the joint pain was described as transient musculoskeletal pain, which was accompanied by flu like symptoms. Pain in the limbs associated with MV-CHIK injection was largely graded as mild (82%), was self-limiting and did not engender any withdrawals from the study. The rate of musculoskeletal pain decreased from 12% (n=5; 67% mild) at the first visit to 2% (n=1; 100% mild) at visit 5. No signs of inflammation were observed.

Severe and serious AEs occurred only for subjects treated with MV-CHIK. All serious AEs reported were non-local and unsolicited. Overall, seven severe AEs occurred (in six participants), of which five were solicited and related to vaccination including headache, local erythema, local induration, local pain and pyrexia.

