**Table 9 Grading of systemic reactions**

Systemic Reaction (General)	Mild (grade 1)	Moderate (grade 2)	Severe (grade 3)	Potentially life threatening (grade 4)
Nausea/vomiting	No interference with activity or 1-2 episodes/ 24 hours	Some interference with activity or >2 episodes/ 24 hours	Prevents daily activity, requires outpatient IV hydration	Emergency room (ER) visit or hospitalization for hypotensive shock
Diarrhea	2-3 loose stools or < 400 gms/ 24hours	4-5 stools or < 400-800 gms/ 24hours	6 or more watery stools or >800 gms/ 24 hours or requires outpatient IV hydration	ER visit or hospitalization
Headache	No interference with activity	Repeated use of non-narcotic pain reliever >24 hours or some interference with activity	Significant; any use of narcotic pain reliever or prevents daily activity	ER visit or hospitalization
Fatigue	No interference with activity	Some interference with activity	Significant; prevents daily activity	ER visit or hospitalization
Myalgia	No interference with activity	Some interference with activity	Significant; prevents daily activity	ER visit or hospitalization
Illness or clinical AE (as defined according to applicable regulations)	No interference with activity	Some interference with activity not requiring medical intervention	Prevents daily activity and requires medical intervention	ER visit or hospitalization
Fever (°C) (°F)	38.0-38.4 100.4-101.1	38.5-38.9 101.2-102.0	39.0-40.0 102.1-104.0	>40.0 >104.0

In addition, any signs and symptoms of arthralgia will be carefully assessed. Importantly, subjects will be asked if they experience any signs of limb pain or joint pain, to distinguish symptoms of arthralgia from flu like symptoms including limb pain.

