### **14.2 Severity Assessment Definitions**

Mild: Transient symptoms, no interference with the subject's daily activities

Moderate: Marked symptoms, moderate interference with the subject's daily activities

Severe: Considerable interference with the subject's daily activities, unacceptable.

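### In the Pain row of Table 8, repeated non-narcotic analgesic use alone satisfies both grade 2 and grade 3, and no text says which grade applies

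*Protocol*

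**What the plan says.** Protocol section 11.2.4, Table 8, defines the grades of local reactions. In the Pain row, grade 2 reads "Interfere with activity or repeated use of non-narcotic pain reliever" and grade 3 reads "Prevents daily activity or repeated use of non-narcotic pain reliever". Section 11.2.5 has the investigator grade the local reactions reported in the diary from that table.

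SAP 2.13.1 has the investigator turn the subject's mild, moderate or severe entry for pain into a grade from 1 to 4. SAP 2.13.2 then keeps the worst grade for summary. SAP Tables 4.32 to 4.35 present the severity of local symptoms from the diary by time-point, diary period and treatment group. Solicited local adverse events are a secondary endpoint (protocol section 4.1.2).

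**The concern.** A severity scale should give a record one grade. Here a subject who takes a non-narcotic analgesic repeatedly for injection-site pain, but whose daily activity is not prevented, meets both definitions. Two investigators who follow the protocol exactly can enter different grades for the same pain. Because the worst grade is kept, one diary day read as grade 3 is enough to move the subject into the severe row for that period.

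What is at stake is the meaning of the severe-pain counts in the diary tables. Severe counts tend to be small, so a few subjects placed by reading habit rather than by symptom can change a row visibly. SAP 2.8 plans no stratification by centre, so site-to-site differences in reading would not show in the tables.

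**Working it through.** The plan states no figure for this point, so there is nothing to reproduce. The check is a comparison of texts, followed by a short illustration of scale.

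**1. Overlap.** Let R be repeated non-narcotic analgesic use.

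- Grade 2 is met by interference with activity, or by R.
- Grade 3 is met by prevention of daily activity, or by R.
- The shared criterion is R. The two cells state no difference in dose, duration or drug class for it.

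**2. Search for a tie-break.**

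- Section 11.2.5 refers to Table 8 and adds no criterion.
- SAP 2.13.1 starts from the subject's three-level rating, but leaves the investigator to interpret it and says nothing about analgesics.
- The worst-grade rule in SAP 2.13.2 works on grades already assigned. It does not choose between two definitions met by one record.
- Section 14.2 defines a severe adverse event as "Considerable interference with the subject's daily activities, unacceptable". It assigns no Table 8 grade.
- Reading in a default does not rescue the row. If the higher grade always wins, the analgesic clause in grade 2 can never decide a grade. If the lower always wins, the clause in grade 3 can never decide one.

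**3. How the protocol treats similar cases.**

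- Table 9, headache, grade 2: "Repeated use of non-narcotic pain reliever >24 hours or some interference with activity". Grade 3: "Significant; any use of narcotic pain reliever or prevents daily activity". Repeated non-narcotic use is grade 2 and narcotic use is grade 3.
- Table 8, itching and induration: non-narcotic use appears in grade 2 only. Grade 3 names a different treatment, an ointment. These rows do not overlap on this ground.
- Phase 1 (section 2.4) graded pain, itching and induration "as moderate if they did compromise activity or necessitated repeated use of non-narcotic pain reliever/anti-inflammatory and pain relieving ointment", and "as severe if they prevented daily activity".

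**4. Scale.** The documents do not say how often subjects use non-narcotic analgesics repeatedly for pain that does not prevent activity. Take p = 1%, 2% or 5% as assumptions.

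- MV-CHIK group of 60: 60 × p = 0.6, 1.2 or 3.0 subjects who fit both grades.
- Control group CV1 or CV2, 20 subjects each: 20 × p = 0.2, 0.4 or 1.0.

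Phase 1 gives only a loose reference for severe pain. It reports seven severe events, "of which five were solicited and related to vaccination including headache, local erythema, local induration, local pain and pyrexia". Five events over five named terms suggests one severe local pain in 42 subjects: 1/42 = 2.4%, exact 95% CI 0.1% to 12.6%. That is 60 × 1/42 = 1.4 per 60, with an upper limit of 60 × 0.126 = 7.6. Phase 1 used volumes up to 1 mL and a two-week diary, against 0.3 mL of MV-CHIK and 7 days here. The reference shows that severe counts are small, but it cannot size the effect.

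**The case against.** The best case against the point is that SAP 2.13.1 begins with the subject's own mild, moderate or severe rating, and analgesic use is noted elsewhere in the diary, under concomitant medication. In many records the subject's rating will settle the grade. This stands, and it narrows the ambiguity. It does not remove it, because the investigator still interprets the entry and is sent to Table 8 to grade it.

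A second objection is that section 11.2.4 calls the scale a modified one, so the grade 3 clause may be deliberate. Phase 1 is mixed evidence on this. It graded repeated ointment use for itching and induration as moderate, and Table 8 moves that to grade 3. What the drafters intended for pain is therefore not proven. The overlap is a fault whatever was intended, since a deliberate grade 3 clause would have required taking the same clause out of grade 2.

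A reader might infer more than the documents support:

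- **Stopping rules.** The rules in section 11.3 that could take in grade 3 local pain concern suspected or treatment-related reactions. Section 13.2 and SAP 8.3 say that solicited events are not assessed for relatedness. The individual rule on solicited events covers systemic ones only. No effect is shown.
- **Bias between arms.** Grading in groups A to D is double-blind (section 6.4), so the choice of grade should not depend on the arm.
- **Figure 4.1 and the SAP 8.3 count of subjects with a severe solicited event.** Both fall under SAP 8.3 and may rest on the adverse-event severity field of section 14.2 rather than on the Table 8 grade. No effect on either is claimed.
- **Comparison with Phase 1.** Neither document plans one for severe pain, and the two studies already differ in formulation, volume and diary length.

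**Conclusion.** The overlap is certain, since it can be read directly in the two Pain cells, and nothing in either document resolves it. Identical pain can be tabulated as moderate or severe in SAP Tables 4.32 to 4.35. Within groups A to D the result is non-differential misgrading of a secondary safety endpoint. The primary endpoint is not affected.

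The size is unknown. The figure of 0.6 to 3.0 subjects per group of 60 depends entirely on the assumed rates of 1% to 5%. It is also the number who could sit in either row, not the number who will be misgraded, because the subject's own rating will settle some of them.

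The severity is minor. The case for acting is that a grading rule is wrong as written and changing one cell puts it right.

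**What to change.** Make the two Pain cells mutually exclusive. Either delete the analgesic clause from the grade 3 cell, or replace it with use of a narcotic pain reliever, as in the Table 9 headache row. Repeated non-narcotic use is then grade 2 only. Notify the sites. Qualifying the grade 2 cell instead would also separate the grades, but would fit the headache, itching and induration rows less well.

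The SAP sets a preliminary analysis for August 2017 and is itself dated May 2018, so some pain records have probably been graded under the present wording. Do not re-examine the grade 3 records alone. That check could only lower the severe count, and would rely on later recall. Choose one of two routes:

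- Apply the corrected rule, blinded to group, to all grade 2 and grade 3 pain records with recorded analgesic use. No described diary field records whether daily activity was prevented, so some records will not be resolvable. Leave their grade unchanged and flag them.
- Leave the grades as they are, and report in the listing how many grade 3 pain records have non-narcotic analgesic use recorded.

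The cost is one protocol amendment, which needs ethics committee approval under section 17.1, and one memo to the sites. Some data will remain graded under the present wording, and the report should say so.

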**Table 9 Grading of systemic reactions**

Systemic Reaction (General)	Mild (grade 1)	Moderate (grade 2)	Severe (grade 3)	Potentially life threatening (grade 4)
Nausea/vomiting	No interference with activity or 1-2 episodes/ 24 hours	Some interference with activity or >2 episodes/ 24 hours	Prevents daily activity, requires outpatient IV hydration	Emergency room (ER) visit or hospitalization for hypotensive shock
Diarrhea	2-3 loose stools or < 400 gms/ 24hours	4-5 stools or < 400-800 gms/ 24hours	6 or more watery stools or >800 gms/ 24 hours or requires outpatient IV hydration	ER visit or hospitalization
Headache	No interference with activity	Repeated use of non-narcotic pain reliever >24 hours or some interference with activity	Significant; any use of narcotic pain reliever or prevents daily activity	ER visit or hospitalization
Fatigue	No interference with activity	Some interference with activity	Significant; prevents daily activity	ER visit or hospitalization
Myalgia	No interference with activity	Some interference with activity	Significant; prevents daily activity	ER visit or hospitalization
Illness or clinical AE (as defined according to applicable regulations)	No interference with activity	Some interference with activity not requiring medical intervention	Prevents daily activity and requires medical intervention	ER visit or hospitalization
Fever (°C) (°F)	38.0-38.4 100.4-101.1	38.5-38.9 101.2-102.0	39.0-40.0 102.1-104.0	>40.0 >104.0

In addition, any signs and symptoms of arthralgia will be carefully assessed. Importantly, subjects will be asked if they experience any signs of limb pain or joint pain, to distinguish symptoms of arthralgia from flu like symptoms including limb pain.

### 11.2.5 Subject diary

The subjects should complete the diary (local, systemic tolerability and adverse events as well as body temperature) after vaccination for 7 days; solicited local and solicited systemic AEs will be assessed by the subjects themselves by checking the presence of the symptoms listed in the subject diary and appropriate measuring of the size of the affected area (a template will be provided for local reaction grading, as shown in the Appendix). The diary will also have space for recording unsolicited AEs and concomitant medication. The assessments will be recorded once daily into a subject diary. Assessments should occur at the same time each day, starting with the day of vaccination. The first entry should be made 6 hours (+/- 1h) after the vaccination. The subject diary will be verified for completeness by the investigator at the

subject's next visit to the study site. The diaries will be collected at the following visit and new ones will be dispensed at each treatment visit. Any AE recorded in the subject diaries will be entered in the eCRF by the investigator or authorized delegates and will only be analyzed when entered in the eCRF. The investigator will assess the severity of the reported local reaction according to the above table and the severity.

### **11.2.6 Laboratory parameters**

The following laboratory parameters will be assessed at time points specified in Table 2 and graded according to the FDA Guidance for Industry: Toxicity Grading Scale for Healthy Adult and Adolescent Volunteers Enrolled in Preventive Vaccine Clinical Trials (Sept. 2007).

The following parameters will be analyzed by local laboratories according to the applicable laboratory SOP:

- Hematology: hemoglobin, hematocrit, erythrocyte count, differential white blood count, platelets.
- Chemistry: creatinine (>1.7 mg/dL), potassium, sodium, calcium, AST, ALT ( $\geq 2.6$  ULN), alkaline phosphatase, bilirubin
- Coagulation parameter: prothrombin time (PT), activated partial thromboplastin time (aPTT), fibrinogen
- Virology: HIV 1/2 Ab if not done within 30 days before screening and HBs-Ag, anti-HBc-Ab and anti-HCV-Ab
- Urinalysis: a standard urine test stick for determining pH-value, glucose, protein, bilirubin, urobilinogen, red blood cells, white blood cells, nitrite, ketone and specific gravity will be used and clinical relevant findings will be noted in the source data and in the eCRF.

**Table 10 Blood sample collection:**

Test	Type of Vials	Volume	Collections
Virology (HIV, HBV, HCV) (all sites)	serum	8 – 10 mL	1x
Immunogenicity 1 and Measles Serology (all sites)	serum	2x 8 - 10 mL	5x (A-D), 7x (M1, M2)
Immunogenicity 2 (all sites except sites in Vienna)	serum	2x 8 -10 mL	5x (A-D), 7x (M1, M2)
T cell Analysis (all sites in Vienna)	(citrate tubes) PBMCs	3x 8-10 mL once 6x 8-10 mL	5x (A-D), 6x (M1, M2)
Shedding whole blood (only AKH Vienna)	EDTA	2 - 3 mL	6x (shedding analysis, A-D only)
Hematology (all sites)	EDTA	3 - 5 mL	3x
Coagulation (all sites)	citrate tubes	3 - 5 mL	3x
Clinical chemistry (all sites)	serum	8 - 10 mL	3x

The total blood volume that will be collected during the entire study:

Sites outside Vienna:	treatment group A, B, C, D: 210 – 270 mL treatment group M1 and M2: 274 – 350 mL
Site AKH in Vienna:	treatment group A, B, C, D: 286 – 368 mL treatment group M1 and M2: 330 – 420 mL
Site Tropical Medicine Vienna:	treatment group A, B, C, D: 274 – 350 mL treatment group M1 and M2: 330 – 420 mL

Laboratory values deviating from the normal ranges will be evaluated by the investigator according to the FDA Guidance for Industry. The values will be graded (mild, moderate, severe) according to the values provided. Clinically relevant deviations have to be reported as adverse events.

NCR = not clinically relevant deviation

CR = clinically relevant deviation

NA = not assessable - laboratory error.

